### **3.3 Justification of the design**

This is primarily a descriptive safety study. All subjects enrolled in this study will have received at least 1 dose of radium-223 dichloride or placebo in the selected feeder trials and will be included in the safety evaluation. The subject population will include subjects treated with placebo and will therefore allow the comparison of the long-term safety profile with and without treatment with radium-223 dichloride.

The procedures chosen for the evaluation of long-term safety in this study population are consistent with the ethical standards used in studies of oncology drugs, and are appropriate for the long-term safety evaluation of subjects from the feeder trials.

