#### 8.3.2.1 Safety analysis

*Section modified by Amendments 1 (Section 13.1) and 2 (Section 13.2.1.2).*

Adverse events will be coded using the standard Medical Dictionary for Regulatory Activities and grouped by system organ class and preferred term. Events will be summarized by frequency and proportion of total subjects, system organ class, and preferred term.

The safety data from feeder trials and 16996 will be combined within each study for all AE summaries. For pooled analyses, all data across the selected feeder trials and 16996 will be combined by treatment groups and by treatment doses, as appropriate. Separate summaries will be given for: all events related to study drug, all events by NCI-CTCAE grade, SAEs, and AEs leading to death.

Deaths and SAEs will be summarized and listed.

The incidence of leukemia, myelodysplastic syndrome, aplastic anemia, and primary bone cancer or any other new primary malignancy; the incidence of bone fractures and bone associated events (e.g., osteoporosis); and for subjects who receive cytotoxic chemotherapy, the incidence of febrile neutropenia or hemorrhage during their chemotherapy treatment and for up to 6 months thereafter, will be summarized using statistical measures that will depend upon whether the study includes a comparator group or is a single-cohort study. Other considerations include the length of follow-up time and time-to-event methods.

Statistical measures that can be used include incidence proportion, incidence rate, and cumulative incidence (or competing risk approach). Definitions of each measure will be described in detail in the SAP.

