The key attribute of radium-223 dichloride is its specific targeting of bone with limited radiation exposure beyond the intended target. However, the proximity of the bone marrow space to site of action of radium-223 dichloride means that there is potential for radiationinduced bone marrow abnormalities. These abnormalities, including bone marrow dysplasia or new primary malignancies, may not become evident until years after the initial exposure to radium-223 dichloride; therefore, longterm follow-up is required to detect them. The ERA 223 study, a phase III randomized trial in prostate cancer participants examining radium-223 dichloride versus placebo in combination with abiraterone and prednisone (study number 15396, NCT02043678) was unblinded based on the Independent Data Monitoring Committee (IDMC) recommendation following an ad hoc independent analysis where more treatmentemergent fractures and total deaths were observed in the active treatment arm compared with the placebo arm. The IDMC also recommended that all bone fractures and bone-associated events (e.g., osteoporosis) occurring in follow-up period are to be documented regardless of investigator's causality assessment. In order to collect comprehensive safety information across all clinical trials with radium-223 dichloride, documentation of fractures (pathological and non-pathological) regardless of relationship, is also implemented in the present trial. In addition, any bone health agent taken during the study period is being collected.

The follow-up period in this study extends to up to 7 years after the last dose of radium-223 dichloride or placebo.

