6.4.2 Adverse Events

Only select categories of post-treatment AEs are to be collected in the long-term follow-up study 16996, including radium-223 dichloride/placebo related AEs and SAEs. The following AE categories identified by the protocol will be evaluated separately:

- New primary malignancies, defined as leukemia, myelodysplastic syndrome, aplastic anemia, primary bone cancer, and any new primary malignancies, regardless of relationship to study drug;
- Bone fractures and bone-associated events:
- Febrile neutropenia and hemorrhage during chemotherapytreatment and for up to 6 months thereafter. A simplified analysis will be performed as specified below
- Pregnancy AEs.

In addition to the above listed select categories of post-treatment AEs collected in study 16996, events related to radium-223 dichloride/placebo by the investigator and ongoing at or occurring from the time of signing of the informed consent and the end of the study were also to be collected by the investigator.

Protocol No.: **BAY 88-8223/16996** Page: 12 of 17

For purposes of the safety analysis of this study, AEs first arising or worsening after signing the 16996 informed consent are defined as 16996-emergent AEs.

AEs will be coded according to the Medical Dictionary for Regulatory Activities (MedDRA) Version 25.1 or higher. When integrating feeder study and 16996 study data, a MedDRA version re-fresh will be performed. The MedDRA version used will be the version in effect per Bayer Standard Operating Procedures (SOPs) at the time of database lock, and will be documented in the study CSR. Differences in MedDRA versions in effect at the time of applicable lock may result in AEs being coded differently between the interim Health Authority reports and the final CSR.

The grade severity of an AE will be documented using the National Cancer Institute (NCI)-Common Terminology Criteria for Adverse Events (CTCAE, Version 4.03).

The set of MedDRA preferred terms (PTs) constituting each category of AEs for analysis purposes will be documented in an appendix to this SAP. The appendix will be approved separately from, and may be approved later than, this SAP.

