Per protocol, febrile neutropenia and hemorrhage AEs are to be collected during and within 6 months of cytotoxic chemotherapy treatment. For the protocol-specified analysis of the incidence of febrile neutropenia or hemorrhage during their chemotherapy treatment and for up to 6 months thereafter, a simplified analysis will be performed, of febrile neutropenia and hemorrhage AEs without regard to cytotoxic chemotherapy association. All 16996-emergent febrile neutropenia and hemorrhage AEs documented in the study CRF will be reported, without regard to chemotherapy treatment.

For the analysis of fractures and bone associated events, separate analyses of patients with bone fractures, patients with bone associated events, and patients with bone fractures and/or bone associated events will be performed. The applicable MedDRA appendix will identify the MedDRA preferred terms applicable to each sub-category.

Unless otherwise specified, the analysis for each AE category will include a summary of the total number and percent of SAF-LTF participants with an AE of the applicable category. Participants with an applicable AE will be summarized by MedDRA preferred term (PT), overall within each applicable MedDRA system organ class (SOC), and overall (any applicable AE), both by worst CTCAE grade and for any grade. For summaries by worst grade, the AE with the worst grade in the applicable summary category will be used. AEs with missing grade will be included in any-grade summaries but not in summaries by worst grade. In addition, listings will be provided.

6.4.2.1 16996-Collected Adverse Events

All AEs collected in study 16996, whether or not collection was required per study 16996 protocol, will be listed for SAF-LTF including AE PT, 16996-emergent (Y/N), start and stop dates, grade, treatment-related (Y/N), serious (Y/N), reason for seriousness, outcome of AE, and time (days) since last dose of study drug. The listing will include all 16996-collected AEs, whether or not emerging within study 16996.

6.4.2.2 16996-Emergent Adverse Events

Summaries of the total number and percent of SAF-LTF participants with an AE of the following categories of 16996-emergent AEs will be presented:

• All 16996-emergent adverse events

Statistical Analysis Plan

Protocol No.: BAY 88-8223/16996

Page: 13 of 17

- Radium-223 dichloride- or placebo-related 16996-emergent AEs;
- Radium-223 dichloride- or placebo-related serious 16996-emergent AEs;

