- 16996-emergent new primary malignancies;
- 16996-emergent bone fractures;
- 16996-emergent serious bone fractures;
- 16996-emergent bone-associated events;
- 16996-emergent serious bone-associated events;
- 16996-emergent pregnancy AEs;
- 16996-emergent febrile neutropenia and hemorrhage without regard to cytotoxic chemotherapy status.

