7.1 Document History

SAP Version	Date	Change	Rationale
1	25 May 2017	Not Applicable	Original version
1 1.1	25 May 2017 01 Apr 2019	Collection and analysis of bone fractures and bone-associated events included Imputation rules for missing AE start dates specified Presentation of systemic anti-cancer medications updated Provision to provide listings in lieu of any tables added, in the event of few reported AEs during 16996	Changes to align the SAP with Amendment 2 of the protocol.
		 Definition of SAF-LTF analysis set 	Additional analysis set for the analysis of 16996-enrolled participants
2	15 FEB 2024	 1. Introduction Specification of duration of follow-up period for breast cancer and prostate cancer studies. Notion no multiple myeloma participants are expected to enter study 16996. 4. Analysis sets Definition of ENR analysis sets Removal of SAF analysis set Description of additional assignment details for participants enrolled in 16996 from non-eligible feeder trials Updated document history table for SAP v1.1 to include SAF-LTF addition 5. General statistical considerations Removal of safety and post-treatment therapy data integration from feeder studies with study 16996 into a longitudinal database Description of limited data (including baseline characteristics and exposure) integration Update and further description of listings presentation 	Additional changes align the SAP with the protocol (Amendment 2), reporting and webposting requirements.

Statistical Analysis Plan

Protocol No · **BAV 88-8223/16996** Page: 15 of 17

I	Protocol No.: BAY 88-8223/16996	Page: 15 of 17
	Definition of premature discontinuation Description of interim safety analyses to meet Health Authority requirements. 6. Statistical methodology Listing of survival assessments Definition of 16996-emergent AEs Description of analyses of safety endpoints and corresponding analysis sets; Additional evaluation of fracture events and incidence of bone-associated events separately Inclusion of demographic and baseline characteristics as well as protocol deviation summaries tables; Specification of categories of AEs for analysis per protocol; Definition of a SAP appendix	Page: 15 of 17
	 Definition of a SAP appendix to include the MedDRA preferred term constituting each category of AE for the safety analyses; Removal of incidence rates and cumulative incidence rates. 	

Consistent use of participants instead of subjects was applied

throughout.

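### SAP version 2 summarizes the primary safety variables only as number and percent, which alone do not separate event rate from time at risk

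*SAP*

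**What the plan says.** SAP 6.4.2 gives the default display for each adverse event category as a "summary of the total number and percent of SAF-LTF participants with an AE of the applicable category", broken down by preferred term, system organ class and worst grade, with listings. SAP 6.4.2.2 applies number and percent to every listed category, including "16996-emergent new primary malignancies", bone fractures, bone-associated events and treatment-related events. The version 2 entry in SAP 7.1 records "Removal of incidence rates and cumulative incidence rates". SAP 7.2, which lists departures from the protocol's planned analyses, does not mention that removal.

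Protocol 8.3.2.1 is permissive: "Statistical measures that can be used include incidence proportion, incidence rate, and cumulative incidence (or competing risk approach"). It also says "Other considerations include the length of follow-up time and time-to-event methods". Protocol 3.3 notes that the population includes placebo subjects and "will therefore allow the comparison of the long-term safety profile with and without treatment with radium-223 dichloride". SAP 5.1 presents summaries by indication, feeder study and arm.

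On time at risk, SAP 6.4.2 states that "AEs first arising or worsening after signing the 16996 informed consent are defined as 16996-emergent AEs", while SAP 5.3 ends follow-up 5 years (breast cancer) or 7 years (prostate cancer) after the last feeder dose. SAP 6.1.1 separately summarizes follow-up from consent to the last known alive date. The listing in SAP 6.4.2.1 gives days since last dose for each event.

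**The concern.** A percent mixes how often events occur with how long people were observed. Arms within one feeder study share the same window, but participants enter it at different consent dates and leave it by death or loss (protocol 4.4.1 withdraws a subject who cannot be contacted for two consecutive 6-month intervals). If arms differ in any of these, equal event rates give unequal percents, and a real difference in rate can be hidden.

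This matters here because both documents expect that some radiation effects "may not become evident until years after the initial exposure to radium-223 dichloride", so the arm that survives longer has more chance to show them. Survival differences between arms are plausible. The documents report longer survival with radium-223 in ALSYMPCA and more deaths in the active arm of ERA 223. Neither is identified as a feeder study, so this shows that a difference could arise, not how large it is here or in which direction.

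**Working it through.** The plan states no event rate, power or sample size to reproduce (protocol 8.4: not applicable). The check is therefore an illustration.

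**Inputs.** From the documents: a 7-year window from last dose (SAP 5.3), with events counted only after consent (SAP 6.4.2). Everything else is assumed: hazard λ, median survival from consent, annual loss, and lag from last dose to consent. T is 7 years minus the lag.

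**Formulas, constant hazard.** μ = ln 2 / median survival; c = −ln(1 − annual loss); k = λ + μ + c.
- Proportion with an event: P = (λ/k)(1 − e^(−kT))
- Person-years (PY) to first event or exit, per participant: (1 − e^(−kT))/k
- Person-time rate = P/PY = λ, whatever the survival or loss

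**1. Constant hazard, 1 per 100 PY in both arms, no loss**

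| Median survival | Consent lag | Percent | Ratio |
|---|---|---|---|
| 2 vs 3 y | 0 (T = 7) | 2.57 vs 3.38 | 1.31 |
| 2 vs 3 y | 2 y (T = 5) | 2.33 vs 2.91 | 1.25 |
| 2 vs 2.25 y | 0 (T = 7) | 2.57 vs 2.80 | 1.09 |

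First row: k = 0.01 + 0.3466 = 0.3566 gives PY = 2.573; k = 0.01 + 0.2310 = 0.2410 gives PY = 3.381. The person-time rate is 1.00 per 100 PY in both arms in every row.

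**2. Same survival, loss 5% vs 10% per year, T = 7.** Median 2 y: 2.31% vs 2.08% (1.11). Median 3 y: 2.98% vs 2.63% (1.13). Median 5 y: 3.77% vs 3.27% (1.15).

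**3. Late-rising hazard, 0.2 then 2.0 per 100 PY from year 3 after last dose, both arms, no loss.** P = 0.002 × PY before year 3 + 0.02 × PY after.
- 2 vs 3 y, lag 0: PY 1.861 + 0.737 vs 2.158 + 1.254, so 1.85% vs 2.94%, ratio 1.59. The overall rate is 0.71 vs 0.86 per 100 PY, ratio 1.21.
- 2 vs 3 y, lag 2 y: PY 0.844 + 1.481 vs 0.892 + 1.999, so 3.13% vs 4.18%, ratio 1.33; overall rate ratio 1.07.
- 2 vs 2.25 y, lag 0: PY 1.861 + 0.737 vs 1.953 + 0.879, so 1.85% vs 2.15%, ratio 1.16.

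Rates within each interval are 0.2 and 2.0 in both arms. A single overall rate therefore does not fully remove the distortion when the hazard rises late.

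**4. Masking.** Take true rates of 0.03 vs 0.02 per year (ratio 1.5), T = 7. If the higher-rate arm exits at 0.45 per year against 0.30, the percents are 6.03 vs 5.58 (1.08). If it exits at 0.60, they are 4.70 vs 5.58 (0.84).

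**5. What a reader can already derive.** Divide the number with an event by N × mean follow-up. Without loss, mean follow-up is (1 − e^(−μT))/μ, which at T = 7 is 2.630 vs 3.469 y for medians of 2 vs 3 y.
- Case 1, first row: 0.978 vs 0.975 per 100 PY, ratio 0.996 (true 1.00).
- Case 2: ratio 0.998 to 0.999 (true 1.00).
- Case 3, first line: ratio 1.207, against 1.212 for the exact overall rate.
- Case 1, first row, at 5 per 100 PY: 4.49 vs 4.41, so 10 to 12% too low in level, with the arm ratio still near 1.

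**The case against.** The case for leaving the plan alone is substantial. Incidence proportion is the first measure that protocol 8.3.2.1 lists, and follow-up length is a consideration, not a requirement. The study is descriptive with no formal testing, and the synopsis calls it single-arm with no control. With death competing, a percent is a legitimate absolute risk: without loss, an Aalen-Johansen cumulative incidence would return the same 2.57% vs 3.38%. Follow-up is summarized by arm, deaths are tabulated and event timing is listed. As step 5 shows, the follow-up table gives nearly the arm ratio that a planned overall rate would give.

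Most of that stands, and it sets the weight of the point. It does not supply an interval estimate. The rough rate is unplanned, counts time after the first event, and runs to the last known alive date, which can fall after the last safety contact. The listing dates each event but gives no person-time by time since dose, so late risk has no denominator.

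Three stronger readings are tempting, and the documents do not support them:
- **That dropping the rates breaches the protocol.** The protocol permits a proportion, and SAP 7.1 discloses the removal even though SAP 7.2 omits it.
- **That the arm percentages will be distorted by 31% or 59%.** Those figures assume consent on the day of last dose and a 50% difference in median survival. No section supports either assumption, and the figures shrink when they are relaxed.
- **That the programme has no rates at all.** SAP 5.5 refers to a supplemental SAP for Health Authority reports. It was not available for this review and may contain them.

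**Conclusion.** The point holds as a cheap improvement. In this SAP the primary safety variables are summarized only by number and percent, and the percent alone does not separate event rate from time at risk. Size and direction in this study are unknown. Under the stated assumptions the spurious percent ratio is 1.09 to 1.31 for the constant-hazard survival scenarios, 1.11 to 1.15 for differing loss, and 1.16 to 1.59 for the late-rising hazard. These are illustrations, not expected bias. The gap is limited to three things: a planned rate with correct person-time, an interval estimate, and a person-time denominator by time since last dose. Confidence is high for the text of this SAP and does not extend to the supplemental one.

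**What to change.** In SAP 6.4.2.2:
- Keep n (%).
- For new primary malignancies, bone fractures, bone-associated events and treatment-related AEs and SAEs, add first 16996-emergent events per 100 PY. Count time from 16996 consent to first event, death or last safety contact, with an exact Poisson 95% CI, by arm within feeder study.
- For new primary malignancies and fractures only, show events and PY in two or three broad intervals since last dose. Count only time after consent, and pool across feeder studies within indication. Label the by-arm pooled display descriptive only, because the feeder mix differs between arms.

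In SAP 6.4.2, state that the percentages are not adjusted for follow-up.

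**Cost.** SAP wording and a few tables. The dates are already held: consent, AE onset (SAP 6.4.2.1), death or last contact (SAP 6.1.4) and last dose (SAP 5.2.1). Intervals will be wide for rare events. In an assumed 2,000 PY, 3 events give 0.15 per 100 PY (0.03 to 0.44) and 20 give 1.00 (0.61 to 1.54). For scale, the roughly 800 expected participants (protocol 3.1) would contribute about 1,660 to 3,480 PY in all, assuming 1 event per 100 PY, median survival 2 to 5 years and loss 0 to 10% per year.

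Finer splits are not worthwhile. With an assumed 80 per arm in case 3 (2 vs 3 y, lag 0), years 5 to 7 hold about 19 vs 38 PY. Zero events there (upper Poisson limit 3.69) would give upper limits of about 19 and 10 per 100 PY.

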### **Definition of serious adverse event**

An SAE is classified as any untoward medical occurrence that, at any dose, meets any of the following criteria (a - g):

- a. Results in death
- b. Is life-threatening

The term ‘life-threatening’ in the definition refers to an event in which the subject was at risk of death at the time of the event, it does not refer to an event which hypothetically might have caused death if it were more severe.

- c. Requires inpatient hospitalization or prolongation of existing hospitalization

A hospitalization or prolongation of hospitalization will not be regarded as an SAE if at least one of the following exceptions is met:

- The admission results in a hospital stay of less than 12 hours
- The admission is pre-planned (e.g., elective or scheduled surgery arranged prior to the start of the study; admission is part of the study procedures as described in Section 7.2).
- The admission is not associated with an AE (e.g., social hospitalization for purposes of respite care)

However, it should be noted that invasive treatment during any hospitalization may fulfill the criterion of ‘medically important’ and as such may be reportable as an SAE dependent on clinical judgment. In addition, where local regulatory authorities specifically require a more stringent definition, the local regulation takes precedence.

- d. Results in persistent or significant disability / incapacity

Disability means a substantial disruption of a person's ability to conduct normal life's functions.

- e. Is a congenital anomaly / birth defect
- f. Is another serious or important medical event as judged by the investigator
- g. Is an occurrence of leukemia, myelodysplastic syndrome, aplastic anemia, and primary bone cancer or any other new primary malignancy (regardless of the investigator's causality assessment)

If disease progression leads to signs and symptoms that meet the criteria for seriousness (e.g., hospitalization), the associated signs and symptoms should be reported as SAEs, not the underlying cause (i.e., "progressive disease" should not be recorded as an SAE). In this case disease progression should be mentioned on the SAE form as an "alternative explanation."

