#### **7.5.1.2.3 Causal relationship**

*Section modified by Amendment 2 (Section 13.2.1.2 and 13.2.1.9).*

Only radium-223 dichloride-/placebo-related AEs and related SAEs will be collected and recorded in this study. All occurrences of leukemia, myelodysplastic syndrome, aplastic anemia, and primary bone cancer or any other new primary malignancy must be reported as SAEs at any time, and regardless of the investigator's causality assessment. All bone fractures and bone associated events (e.g., osteoporosis) should be collected as either AEs or SAEs if the criteria of SAE were met, regardless of the investigator's causality assessment.

The assessment of the causal relationship between an AE and the radium-223 dichloride/placebo treatment is a decision to be made by the investigator, who is a qualified physician, based on all information available at the time of the completion of the eCRF.

The assessment is based on the question whether there was a “reasonable causal relationship” to radium-223 dichloride/placebo.

Possible answers are “yes” or “no”

An assessment of “no” would include:

1. The existence of a highly likely alternative explanation, e.g., mechanical bleeding at surgical site.

or

2. Non-plausibility, e.g., the subject is struck by an automobile when there is no indication that the drug caused disorientation that may have caused the event; cancer developing a few days after the first drug administration.

An assessment of “yes” indicates that the AE is reasonably associated with the use of radium-223 dichloride/placebo.

Important factors to be considered in assessing the relationship of the AE to radium-223 dichloride/placebo include:

- The temporal sequence from drug administration during the feeder trial:  
The event should occur after the drug was given. The length of time from drug exposure to event should be evaluated in the clinical context of the event.
- Underlying, concomitant, intercurrent diseases:  
Each event should be evaluated in the context of the natural history and course of the disease being treated and any other disease the subject may have.
- Concomitant medication or treatment:  
The other drugs the subject is taking or the treatment the subject receives should be examined to determine whether any of them might have caused the event in question.
- Known response pattern for this class of drug: clinical / preclinical
- Exposure to physical and / or mental stresses:  

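### The SAP's row for all 16996-emergent AEs mixes a required core with incompletely collected events, so it should not be read as total AE burden or compared across feeder studies

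*SAP*

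**What the plan says.** **Scope of collection.** SAP Section 6.4.2 states: "Only select categories of post-treatment AEs are to be collected in the long-term follow-up study 16996". Protocol Section 7.5.1.2.3 states: "Only radium-223 dichloride-/placebo-related AEs and related SAEs will be collected and recorded in this study". It then makes exceptions, whatever the causality, for the listed malignancies and blood disorders and for bone events. The AE definition in protocol Section 7.5.1.1 has the same structure and adds febrile neutropenia and hemorrhage in participants given cytotoxic chemotherapy.

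**Definition of emergence.** SAP Section 6.4.2: "AEs first arising or worsening after signing the 16996 informed consent are defined as 16996-emergent AEs". This is a timing rule only.

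**Listing.** SAP Section 6.4.2.1: "All AEs collected in study 16996, whether or not collection was required per study 16996 protocol, will be listed". The SAP thus expects non-required events in the database.

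**Table.** SAP Section 6.4.2.2: "Summaries of the total number and percent of SAF-LTF participants with an AE of the following categories of 16996-emergent AEs will be presented". Ten rows follow. The first is "All 16996-emergent adverse events", with no further restriction. The other nine are limited to treatment-related events or to a named category.

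**Progression symptoms.** When progression causes serious signs or symptoms, protocol Section 7.5.1.1 says that "the associated signs and symptoms should be reported as SAEs, not the underlying cause". The opening of Section 7.5.1.4 repeats this. Both ask for progression to be entered on the form as another explanation, and neither requires relatedness.

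**The concern.** A percentage needs a defined numerator. Here the denominator is clear (SAF-LTF), but the numerator has two parts. One part is events every site must record. The other is events that reach the database only where a site chose to record them, or followed one protocol passage rather than another. A row whose label begins with the word All invites reading as total AE burden, which a study with selective collection cannot measure.

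More than one cell is affected. Unless otherwise specified, SAP Section 6.4.2 breaks each AE category down by preferred term, system organ class and worst grade, so the incompletely collected events carry into those tables. SAP Section 5.1 presents summaries by indication, feeder study and arm, which puts feeder studies with possibly different recording habits next to each other. There is no row for all serious AEs, so unrelated serious progression symptoms that fall outside the named categories would surface mainly here.

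**Working it through.** The documents give no expected percentage for this row, no sample size calculation and no formal test, so there is no planned figure to reproduce. The check is mainly textual.

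**Step 1. Can a non-required event enter the row?** The row needs an AE that is 16996-emergent. Emergence is timing only (SAP 6.4.2). The SAP's own use of the term AE includes events whose collection was not required (SAP 6.4.2.1). Section 6.4.2.2 adds no filter. Entry into the row is therefore an inference, since the explicit wording belongs to the listing, but nothing in the table specification blocks it.

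**Step 2. Does the protocol itself generate such events?**

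| Rule | Where | Effect on an unrelated serious progression symptom |
|---|---|---|
| AE definition for this study | Protocol 7.5.1.1 | Not an AE unless related or in a named category |
| Collection limited to related events, with exceptions | Protocol 7.5.1.2.3 | Not collected |
| 24-hour notification limited to related SAEs, listed malignancies and blood disorders, and serious bone events | Protocol 7.5.1.4, investigator's notification | Not notified |
| Progression symptoms meeting seriousness criteria | Protocol 7.5.1.1 (SAE definition) and opening of 7.5.1.4 | Reported as an SAE; no relatedness condition |

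Under Section 7.5.1.2.3, a very probable other cause leads to a causality answer of no. A symptom attributed to progression will often be judged unrelated, although naming progression does not settle the answer by itself. Two sites acting in good faith can therefore treat the same event differently.

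**Step 3. Illustration of sensitivity (assumed inputs, not document values).** Let r be the proportion with a required event, u the proportion with an unrelated serious progression symptom, and c the share of the latter recorded. Assuming independence:

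row = 1 − (1 − r)(1 − u·c)

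With r = 0.20, u = 0.50, and the approximately 800 participants expected in protocol Section 3.1:

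| c | Row | Participants |
|---|---|---|
| 0 | 1 − 0.80 × 1.000 = 20% | 160 |
| 0.25 | 1 − 0.80 × 0.875 = 30% | 240 |
| 0.50 | 1 − 0.80 × 0.750 = 40% | 320 |
| 0.75 | 1 − 0.80 × 0.625 = 50% | 400 |
| 1 | 1 − 0.80 × 0.500 = 60% | 480 |

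Two feeder studies with identical true risks but recording shares of 0.25 and 0.75 would show 30% and 50%, a gap of 20 points from recording alone.

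**Step 4. Range.** The shift from c = 0 to c = 1 is (1 − r)·u. Over r from 10% to 30% and u from 30% to 70%, it runs from 0.70 × 0.30 = 21 points to 0.90 × 0.70 = 63 points. The row itself runs from 10–30% with none recorded to 37–79% with all recorded. The width shows that the documents do not fix the size.

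**The case against.** The strongest reply has five parts.

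- **The row is secondary.** It is not among the primary variables in SAP Section 3.1, and each primary category has its own row limited to related events or a defined set of terms. This stands, and it limits the consequence.
- **The row can be read within the protocol's study-specific AE definition,** which would exclude non-required events. That reading is possible, but SAP Section 6.4.2.1 applies the term AE more widely, and Section 6.4.2.2 does not say which usage governs.
- **The progression clauses may only say which term to report,** and most protocol passages consistently limit SAEs to related ones. This is a fair reading and weakens the conflict. It does not remove it, because the clauses state no relatedness condition. The synopsis methodology wording also leaves unclear whether the relatedness condition covers SAEs.
- **Differences between randomised arms are unlikely to be created this way.** Arms of one feeder study generally share sites, so uneven recording should mostly dilute a contrast. This stands: a reader might infer that arm differences in this row are artefacts of recording, and the documents do not support that. Comparison across feeder studies is more exposed.
- **The analysis is descriptive.** This is true, but a descriptive percentage still needs a defined numerator.

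A reader might also infer that the row is nothing more than what sites chose to record, or that sites record every AE and the row becomes very high. Neither follows. Related events and the named categories are mandatory, and the documented mechanism concerns serious progression symptoms, not wholesale over-recording.

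**Conclusion.** The concern holds in limited form. As specified, the first row of SAP Section 6.4.2.2 and its term, class and grade breakdowns combine a mandatory core with an incompletely collected remainder. The row is neither total AE incidence nor the incidence of the AEs the protocol requires. It should not be read as overall AE burden or compared across feeder studies. The restricted rows do not depend on it, and no primary variable is affected.

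The conclusion rests on the missing filter, on the SAP's expectation of non-required events, and on the unresolved protocol passages. The size cannot be derived from the documents. The 20% to 60% span and the 21 to 63 point range are illustrations under assumed rates and independence, not estimates. The documents do not show how often sites record such events.

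**What to change.** **SAP Section 6.4.2.2.** Replace the first row with: *Any 16996-emergent AE that is radium-223/placebo-related or in a SAP-defined category (new primary malignancy, bone fracture or bone-associated event, febrile neutropenia/hemorrhage as analysed, pregnancy)*. Apply the same restriction to its breakdowns. Keep all other recorded AEs in the Section 6.4.2.1 listing, and add one separate row for them, footnoted as not systematically collected.

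The flag is the union of the relatedness field and the preferred-term sets already planned for the SAP's MedDRA appendix. It needs no chemotherapy linkage. One residue should be footnoted: the SAP counts febrile neutropenia and hemorrhage regardless of chemotherapy, so events outside the protocol's window can still enter if recorded.

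**Protocol.** The sponsor should reconcile the progression clauses in the Section 7.5.1.1 SAE definition and the opening of Section 7.5.1.4 with the Section 7.5.1.1 AE definition, Section 7.5.1.2.3 and the notification paragraph of Section 7.5.1.4. This review takes no position on which rule is right.

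**Cost.** One derived flag, one extra footnoted row, and a smaller percentage in the first row. A protocol clarification may need ethics review and cannot change how past events were recorded, but the SAP change works without it.
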